13 DATA ANALYSIS AND STATISTICAL CONSIDERATIONS

13.1 Description of statistical methods

All statistical aspects of the study will be fully documented in a comprehensive Statistical Analysis Plan authored by the study statistician and agreed by the independent Trial Steering Committee.

The primary outcome will be an exploration of camostat safety and toxicity, in terms of the number and severity of AEs and SAEs.

Descriptive statistics will be used to describe the demographics for each randomised group and overall. For categorical data, frequencies will be reported, and for continuous variables means and standard deviations, or for skewed data, medians and interquartile ranges will be reported.

Secondary outcomes will be reported in a similar way to the demographic data, with an estimate of the difference and standard error between the treatment groups for continuous or ordinal scale data. Medians and IQRs will be used where data are non-normally distributed. Absolute percentage difference and standard error will be reported for binary variables. Kaplan-Meier plots and life tables will be used to estimate median survival times

Subgroups will be explored where there are sufficient patients in each group. Data will be split by age (< 65 years vs ≥ 65 years), fall in lymphocyte ($<20\%$ fall vs $\geq 20\%$ fall), and neutrophil:lymphocyte ratio (<2.18 vs ≥ 2.18) for key explanatory variables.

No significance testing will be performed. Differences between treatment groups will be reported solely to inform future trials.

All enrolled patients who receive at least one dose of camostat in the treatment arm and complete Day 1 in the control arm will be evaluable for safety.

In order to be evaluable for efficacy, treatment arm patients must receive camostat for a minimum of five days, and control arm patients must either complete up to Day 14 or come off trial at an earlier timepoint due to an endpoint (e.g. hospitalisation).

Safety data will be collected from the date of written, or verbal, consent. Safety variables will be summarised by descriptive statistics.

Adverse events will be reported as tables of frequency of AEs by MedDRA system organ class and by worst severity grade observed. Tables should indicate related and unrelated events

Adverse events will be reported for each arm and presented as tables of frequency of AEs by MedDRA system organ class and by worst severity grade observed. Tables should indicate related and unrelated events.

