3. TRIAL OBJECTIVES

Primary Objective and Endpoint	
Objective	Endpoint
To further assess the safety and toxicity profile of camostat, to support integration into a Phase III trial.	Causality and severity of each adverse event (AE) to camostat.
Secondary Objectives and Endpoints	
Objective	Endpoint
To confirm that the PK profile aligns with the established PK profile for the active metabolite of camostat, 4-(4-Guanidinobenzyloxy)phenylacetic acid (GBPA).	Confirm PK parameters of GBPA as assessed by population estimates from population PK analysis (popPK).
To assess the ability of camostat to reduce the requirement for COVID-19 related hospital admission in community patients with SARS-CoV-2 infection.	Rate of COVID-19 related hospital admission in community patients with SARS-CoV-2 infection.
To evaluate the requirement for supplementary oxygen (non-invasive or mechanical invasive) in patients who have received camostat as treatment for SARS-CoV-2 infection.	Supplementary oxygen-free days at 28 days (from randomisation).
To evaluate the requirement for ventilation in patients who have received camostat as treatment for SARS-CoV-2 infection.	Ventilator-free days at 28 days (from randomisation).
To evaluate efficacy of camostat by effect on COVID-19 related clinical improvement.	
Time Frame: Days 1-28
 
Time to worst point on the scale or deterioration of two points or more (from randomisation) on a 9-point category ordinal scale.
 
9-point category ordinal scale:
 
 0. Uninfected, no clinical or virological evidence of infection 1. Ambulatory, no limitation of activities 2. Ambulatory, limitation of activities 3. Hospitalised – mild disease, no oxygen therapy 4. Hospitalised – mild disease, oxygen by mask or nasal prongs 5. Hospitalised – severe disease, non-invasive ventilation or high-flow oxygen

	
 6. Hospitalised – severe disease, intubation and mechanical ventilation 7. Hospitalised – severe disease, ventilation and additional organ support – vasopressors, renal replacement therapy (RRT), extracorporeal membrane oxygenation (ECMO) 8. Death
Research Objectives and Endpoints	
Objective	Endpoint
[REDACTED]	
 - [REDACTED] - [REDACTED] - [REDACTED] - [REDACTED]
[REDACTED]	
 - [REDACTED] - [REDACTED] - [REDACTED] - [REDACTED]

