6.7 Adverse Events

For patients on the treatment arm Pre-treatment AE's will be defined as those where "Did this AE start prior to first dose of IMP?" is ticked. Treatment Emergent AE's will be defined as those where "Did this AE start prior to first dose of IMP?" is not ticked. For patients on the control arm pre-treatment AE's will be defined as those where the AE started prior to Day 1. Treatment emergent AE's will be defined as those where the AE started after and inclusive of Day 1.

Treatment related AE's are those where causality to IMP is considered to be Possible, Probable or Highly Probable.

COVID-19 related AE's will be defined as those where "Is this AE related to COVID-19" is ticked yes.

The frequency of AEs will be summarised overall and by treatment arm. A patient can be counted multiple times per row for the No. of Episodes but will only be counted once per row for the No. of Patients.

Table 5: Frequency of All Adverse Events

Safety population

MedDRA System Organ Class (SOC) MedDRA Preferred Term	No. of Episodes Reported	No. of Patients N=XX	No. of Patients in Treatment Arm N=XX	No. of Patients in Control Arm N=XX
All AE's	N	N (%)	N (%)	N (%)
BLOOD AND LYMPHATIC...				
Anemia				
CARDIAC DISORDERS				
Sinus tachycardia				
Etc				

There will be additional versions of the above table based on pre-treatment AE's, treatment emergent AE's, treatment emergent SAE's (any AE that is considered Serious), related treatment emergent AE's. COVID-19 related AE's.

Overview of treatment emergent adverse events (by treatment arm). An AE is considered to have led to withdrawal if an adverse event with "Did the AE cause the subject to be discontinued from the study?" is recorded as yes.

Table 6: Overview of Treatment Emergent Adverse Events (Inclusive and post Day 1)

Safety population

Patients with TEAEs	Overall No. of Patients N=XX	No. of Patients in Treatment arm N=XX	No. of Patients in Control arm N=XX
Patients with >=1 TEAE	N (%)	N (%)	N (%)
Patients with >= 1 TE SAE			
Patients with >= 1 COVID-19 related			
Patients with >= 1 Treatment related			
Patients with >= 1 AE leading to withdrawal			
Patients who died			

Treatment emergent adverse events leading to withdrawal of treatment will be listed by patient. Patients will be included if an adverse event has "Action taken" recorded as "Drug Withdrawn" or "Did the AE cause the subject to be discontinued from the study?" is recorded as yes.

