8 TABLES LISTINGS AND FIGURES

8.1 LISTINGS:

Completed or Discontinued patients

Treatment compliance End of monitoring period (Control arm)

End of study

Protocol deviations

Patients excluded from efficacy analysis

Screening failures

EnrolmentDemographic and Baseline Data

Demographics

Randomisation

Medical history

Risk factors

COVID-19 symptoms

Influenza or COVID-19 Vaccination

Concomitant medications

Medical procedures

Compliance and/or Drug Concentration Data

Treatment compliance Efficacy Response Data

9-point ordinal scale for clinical improvement

COVID-19/Camostat related hospitalisation details

Oxygen therapy and ventilation

Hospitalisation follow up

Safety Data

Adverse Events (by subject)

Adverse Events by SOC

Pregnancy test

Laboratory results

Imaging

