8.2 TABLES

Demographic Data

Baseline characteristics by treatment arm

Reasons for patient withdrawal / completion

Compliance

Treatment modifications and/or non-compliance (treatment arm only)

Efficacy Data

Ordinal Scale

Summary of Secondary Endpoint Data

Safety Data

Overview of Treatment Emergent Adverse Events (Inclusive and post Day 1)

Frequency of All Adverse Events

Frequency of pre-treatment AEs

Frequency of TEAEs

Frequency of All Camostat related treatment emergent AEs

Frequency of all COVID-19 related treatment emergent AEs

Frequency of all treatment emergent SAEs

Breakdown of TEAEs leading to Patient withdrawal

Neutrophils:Lymphocytes ratio per patient (treatment and control arm respectively)

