10 STATISTICAL METHODS SECTION FROM THE PROTOCOL

The primary outcome will be an exploration of camostat safety and toxicity, in terms of the number and severity of AEs and SAEs. Recruitment rate will be reported as numerator and denominator, with the percentage and exact binomial 95% confidence interval. The other feasibility measures will be reported in the same way.

Descriptive statistics will be used to describe the demographics for each randomised group and overall. For categorical data, frequencies will be reported, and for continuous variables means and standard deviations, or for skewed data, medians and interquartile ranges will be reported.

Secondary outcomes will be reported in a similar way to the demographic data, with an estimate of the difference and standard error between the treatment groups for continuous or ordinal scale data. Medians and IQRs will be used where data are non-normally distributed. Absolute percentage difference and standard error will be reported for binary variables. Kaplan-Meier plots and life tables will be used to estimate median survival times.

Subgroups will be explored where there are sufficient patients in each group. Data will be split by age (< 65 years vs ≥ 65 years), fall in lymphocyte (<20% fall vs $\geq 20\%$ fall), and neutrophil:lymphocyte ratio (<2.18 vs ≥ 2.18) for key explanatory variables.

No significance testing will be performed. Differences between treatment groups will be reported solely to inform future trials.

All enrolled patients who receive at least one dose of camostat in the treatment arm and complete Day 1 in the control arm will be evaluable for safety.

In order to be evaluable for efficacy, treatment arm patients must receive camostat for a minimum of five days, and control arm patients must either complete up to Day 14 or come off trial at an earlier timepoint due to an endpoint (e.g. hospitalisation).

Safety data will be collected from the date of written or verbal consent. Safety variables will be summarised by descriptive statistics.

Adverse events will be reported as tables of frequency of AEs by MedDRA system organ class and by worst severity grade observed. Tables should indicate related and unrelated events

Adverse events will be reported for each arm and presented as tables of frequency of AEs by MedDRA system organ class and by worst severity grade observed. Tables will indicate related and unrelated events

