12 LIST OF ANALYSES

Although the sample size has been calculated on recruitment rate, the primary outcome will be the comparison of adverse events and their severity between treatment arms. These will be listed overall and by strata.

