12.2 Main study findings

The primary outcomes for this trial are safety and adverse events. These will be tabulated by treatment group and by strata/subgroups. Pregnancy, compliance, protocol deviations will also be tabulated in this way.

The majority of secondary outcomes will be reported in the main RAP. The secondary outcomes of number of oxygen-free days, ventilator-free days, and number of days to worst point on the 9-point ordinal scale (see secondary objectives in RAP for definitions) will be reported as median and range for the 28 days of follow up post-randomisation.

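### Two AE table shells do not fully deliver the between-arm comparison: Table 5 pools episodes over arms, and Table 6 can miss patients who stop camostat for an AE

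*SAP*

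**What the plan says.** The SAP file consists of a reporting plan (RAP) with the statistical analysis plan as an appendix. Protocol 13.1 describes the primary outcome "in terms of the number and severity of AEs and SAEs". RAP 3 gives the endpoint as "Causality and severity of each adverse event (AE) to camostat". SAP 12 says that "the primary outcome will be the comparison of adverse events and their severity between treatment arms", and SAP 12.2 adds: "These will be tabulated by treatment group and by strata/subgroups". SAP 12.4 leaves the tabular outputs to the RAP, so the RAP 6.7 shells carry the primary outcome in the clinical study report (CSR).

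- **Table 5** has one column of episodes for the whole trial, then columns of patients overall, in the treatment arm and in the control arm. On repeats the rule is: "A patient can be counted multiple times per row for the No. of Episodes". RAP 8.2 lists six tables in this format: all AEs, pre-treatment, treatment-emergent, camostat-related, COVID-19-related, and "Frequency of all treatment emergent SAEs".
- **Table 6** is the by-arm overview of treatment-emergent AEs. Its withdrawal row is defined by the question whether the AE caused discontinuation from the study.
- **Table 7** lists patients one by one. It takes a patient if that question is answered yes or if the action taken was withdrawal of the drug, and it has a separate column for each.
- **RAP 7.3** gives numbers of events by arm, but only in the registry templates, which RAP 7 keeps out of the CSR.

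**The concern.** The number of AEs is part of the stated primary outcome, and the RAP chooses to count repeat episodes, yet it reports that count only for both arms together. A CSR reader can compare how many patients were affected in each arm, but not in general how many events each arm had.

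For withdrawals, two adjacent paragraphs of RAP 6.7 use different rules under nearly the same name. The narrower rule feeds the by-arm overview and the wider one feeds the listing. Table 6 could then show fewer AE withdrawals on camostat than Table 7 lists, with nothing in the shell to explain the gap. The trial is descriptive and its safety tables are meant to support integration into a Phase III trial, so the tables are themselves the result.

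**Working it through.** The documents give no AE rate, number of episodes or number of withdrawals, so there is no planned figure to reproduce. The arm size (up to 50, from RAP 4) is theirs; the counts below are assumptions chosen to show the range.

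**1. Which Table 5 versions are affected.**

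| Version | Does the pooled episode column obscure the arm comparison? |
|---|---|
| All AEs | Yes |
| Treatment-emergent AEs | Yes |
| COVID-19-related AEs | Yes |
| Treatment-emergent SAEs | Yes |
| Camostat-related AEs | In effect no: protocol 12.2 ties every related category to the timing of camostat administration, and protocol 5.3.1 gives control patients best supportive care |
| Pre-treatment AEs | Not relevant to a treatment comparison |

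Four of the six are affected.

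**2. How far the split can be recovered.** Let S_t and S_c be the sums, over preferred terms, of patients affected in the camostat and control arms, and let E be the pooled episodes. Each affected patient contributes at least one episode to a term, so the repeats are R = E − S_t − S_c. A term seen in one arm only is fully attributable to that arm. If all repeats fall in terms seen in both arms, camostat episodes lie between S_t and E − S_c; otherwise the range is narrower. With E = 60:

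| S_t + S_c | R | Camostat episodes | Camostat:control ratio |
|---|---|---|---|
| 30 + 30 | 0 | 30 | 1.00 exactly |
| 28 + 28 | 4 | 28 to 32 | 28/32 = 0.88 to 32/28 = 1.14 |
| 25 + 25 | 10 | 25 to 35 | 25/35 = 0.71 to 35/25 = 1.40 |
| 20 + 20 | 20 | 20 to 40 | 20/40 = 0.50 to 40/20 = 2.00 |

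In the third row the difference is ±10/50 = ±0.20 episodes per patient with 50 per arm. The last row is an extreme case: a third of all episodes would be same-term repeats, all in terms seen in both arms.

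**3. The Table 6 row.** Table 6 counts a patient if the study flag is yes. Table 7 lists a patient if the study flag is yes or the drug was withdrawn. The difference is the k patients whose drug was withdrawn for an AE without the study flag. The camostat percentage is then too low, as a measure of AE-driven stops, by k/n:

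| k | n = 50 | n = 40 | n = 30 |
|---|---|---|---|
| 1 | 2.0 points | 2.5 | 3.3 |
| 3 | 6.0 | 7.5 | 10.0 |
| 5 | 10.0 | 12.5 | 16.7 |

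**4. Can k be above zero?** Protocol 5.3.3 provides for withdrawal of treatment when an event is judged at least possibly caused by camostat, which makes the case foreseeable. Protocol 12.3 asks for an end-of-study assessment after removal from treatment for an AE, so some or all such patients may also carry the study flag. The documents do not settle k.

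**The case against.** **On episodes.** No section promises episode counts by arm in a CSR table. Patients with an event, given by arm with percentages, are the usual safety summary and Table 5 delivers them. Event counts by arm are already planned for the registry, and the by-subject listing covers at most 100 patients. All of this is true and keeps the point modest. It does not remove it: the number of AEs is in the primary outcome, and the registry tables are outside the CSR.

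**On withdrawals.** Study discontinuation is the only withdrawal measure that can be compared with an untreated control, and the rule for Table 6 is stated openly. Table 7 names the patients, and camostat withdrawal can arise only in one arm, so that column needs no arm split. RAP 6.1 promises counts of reasons for treatment discontinuation, and Table 2 has an AE/SAE row by arm. This stands as a reason to keep the existing row. It does not explain why the overview and the listing disagree, or why the overview has no row for AE-driven camostat stops.

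**Stronger readings that the documents do not support.** A reader might infer that Table 6 leaves out all AE-driven camostat stops; it leaves out only those not also flagged as study discontinuation. The protocol section 11 remark that stopping treatment is not withdrawal from follow-up concerns a patient's own decision, so it is weak evidence on AE-driven stops. A reader might also infer that severity is missing from the plan, since none of the eight AE tables in RAP 8.2 shows it. But protocol 13.1 and SAP 10 promise tables for each arm, "presented as tables of frequency of AEs by MedDRA system organ class and by worst severity grade observed". RAP 2 says that the RAP supplements the protocol, and the RAP 8.2 list is not exhaustive: it omits the deviation summary promised in RAP 6.4. What is missing is a shell, not the analysis.

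**Conclusion.** The point holds for two shells and is worth acting on before the tables are programmed. Numbers of patients with AEs, SAEs and related AEs are delivered by arm. Not delivered in the CSR tables are, first, the number of events per arm in four Table 5 versions when a term has repeats and occurs in both arms; and second, in the Table 6 overview, any patient who stops camostat for an AE without also being flagged as discontinued from the study.

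The episode ambiguity runs from none (no repeats) to a ratio of 0.71 to 1.40 with 10 repeats among 60 episodes, on assumed counts. The Table 6 gap is 2.0 points per patient with 50 in the arm, with frequency unknown. Treating the camostat-related version as attributable assumes that no control-arm event is recorded as related to camostat. A reader might take these gaps as bias in the safety results. The documents do not support that: the data are collected, no significance testing is planned under protocol 13.1, and no estimate or error rate changes.

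**What to change.** 1. In Table 5 and its versions, show episodes as well as patients separately for each arm.
2. In Table 6, relabel the existing row as AE leading to study discontinuation. Add a row for AE leading to camostat withdrawal (action taken recorded as drug withdrawn; treatment arm only), so that the two rows match the two columns of Table 7.
3. Editorial only: add to RAP 6.7 and the RAP 8.2 list a shell for the table already promised in protocol 13.1 and SAP 10, by arm, system organ class and worst severity, split into related and unrelated events.

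The cost is shells and programming. Protocol 12.3 already has severity, relatedness and action taken recorded, and RAP 6.7 already uses the study-discontinuation question, so no new data are needed.

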6.8 Laboratory results

Full set of Laboratory results will be presented in the listings per patient. Additional tables to represent Neutrophils:Lymphocytes ratio per patient will be presented as follows:

Table 8: Neutrophils:Lymphocytes ratio per patient (Treatment arm)

*Baseline to be included

		Neutrophils:Lymphocytes ratio (10^9/L)		
Patient Number		Screening	Day 7	Day 14

Table 9: Neutrophils:Lymphocytes ratio per patient (Control arm)

*Baseline to be included

Patient Number	Neutrophils:Lymphocytes ratio (10 ⁹ /L)		
	Screening	Day 7	Day 14

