3.3.1 Adverse events

Camostat has been in clinical use for over 30 years in Japan and Korea and has a known, acceptable safety profile. Adverse reactions reported during the safety surveillance of camostat for its licensed indications include shock or anaphylactoid symptoms, thrombocytopenia, changes in liver enzymes, gastrointestinal disorders, rash and hyperkalaemia, all with low reported incidences (<1% patients).

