12.6 Specific Events of Interest

The following events will be closely monitored as trial specific events of interest:

- Shock or anaphylactoid symptoms such as decreased blood pressure, dyspnoea and pruritis
- Rash, pruritis
- Gastrointestinal events (nausea, abdominal discomfort, abdominal distension)
- Changes in liver enzymes (AST, ALT, GGT) or jaundice
- Thrombocytopenia
- Hyperkalaemia

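### Measured liver enzymes, platelets and potassium are only listed per patient; with no by-arm summary specified, the comparison rests on which abnormalities are recorded as AEs in an open-label trial

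*SAP*

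**What the plan says.** Protocol section 12.6 opens its list with "The following events will be closely monitored as trial specific events of interest". Three of the entries are laboratory quantities: "Changes in liver enzymes (AST, ALT, GGT) or jaundice", "Thrombocytopenia" and "Hyperkalaemia". Protocol 8.1 and 8.3.2 schedule platelets, potassium, ALT, AST and GGT at baseline and on Days 7 and 14, with no restriction by arm.

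For presentation, section 6.8 of the reporting plan states: "Full set of Laboratory results will be presented in the listings per patient". It continues: "Additional tables to represent Neutrophils:Lymphocytes ratio per patient will be presented as follows". Those ratio tables (Tables 8 and 9) have one row per patient, one table per arm and no summary row. The list of tables in section 8.2 has no other laboratory item. Section 12.4 of the appended SAP adds medians for three efficacy variables, a Kaplan-Meier plot and optional daily plots, but no laboratory summary.

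Several general statements point the other way. Protocol 13.1 and the appended SAP (sections 10 and 11.1) say that safety variables will be described with summary statistics. Section 6.10 groups data by assigned arm and summarises continuous variables. Section 6.6 says that laboratory results will be taken into account for safety, without saying how, and leaves room for further safety analyses.

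**The concern.** The primary objective is the safety and toxicity profile of camostat. The laboratory values most relevant to the known reactions are scheduled in both randomised arms, yet the stated output is a listing. A reader who wants to know whether ALT rose more on camostat than under supportive care would have to compile the answer from patient-level rows.

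A by-arm comparison of these effects does exist, through AE preferred terms. But a laboratory value enters it only when someone decides that it is an AE, and in an open-label trial that decision is made knowing the arm. If abnormal values are recorded more readily in one arm, the AE table shows a difference that the measurements might not. If they are recorded too rarely in both, it shows nothing. The measured values at scheduled visits do not pass through that filter.

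**Working it through.** **1. Does any specified output summarise these analytes by arm?**
- Section 6.8: listing, plus per-patient neutrophil:lymphocyte tables. No.
- Section 8.2: the neutrophil:lymphocyte ratio is the only laboratory table. No.
- Appended SAP 12.4: efficacy variables and optional plots of daily data. No.
- Protocol 13.1 and section 6.10: a general promise of summaries, with no laboratory output that carries it out.

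**2. What does the AE route compare, and what does it depend on?**
- Protocol 12.1.1 lets an abnormal laboratory finding count as an AE and collects AEs in both arms.
- Table 5 (section 6.7) counts patients by preferred term in each arm. Recorded hyperkalaemia, thrombocytopenia or raised ALT would appear there.
- Protocol 12.3 grades severity as mild, moderate or severe by investigator judgement. No numerical laboratory threshold for an AE is given; the cut-offs in protocol 6.2 are for eligibility.
- For patients recruited in hospital, protocol 12.3 records expected deterioration as an AE only if it is judged to have worsened unexpectedly.
- Protocol 5.3.3 has camostat interrupted and blood taken when a clinically significant abnormality is found. Control patients have no drug to interrupt, so laboratory follow-up can differ by arm.

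**3. Precision of a by-arm summary.** The plan gives no precision figure for laboratory data. Its only sizing figure is the recruitment rate: SE = √(0.5 × 0.5 / 200) = 3.5%, which reproduces the stated value if 100 recruited at 50% means 200 approached. It has no bearing here.

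Inputs: up to 50 patients per arm (section 4, Table 1); 40 per arm as an assumed lower case, because protocol 8.3.2 allows sampling to be waived. SD is that of the quantity compared.
- SE of the difference in means = SD × √(2/n).
- n = 50: √(2/50) = 0.20 SD; half-width 1.96 × 0.20 = 0.39 SD.
- n = 40: √(2/40) = 0.224 SD; half-width 1.96 × 0.224 = 0.44 SD.

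**4. Would it help with rare reactions?** Protocol 3.3.1 puts these reactions below 1% in licensed use.
- Chance of at least one case in 50 at a true rate of 1%: 1 − 0.99^50 = 39.5%. At 0.5%: 1 − 0.995^50 = 22.2%.
- Exact two-sided 95% upper limit after 0 of 50: 1 − 0.025^(1/50) = 7.1%.
- A shift table also counts patients, so a shift with a 1% rate has the same 39.5% chance of appearing.
- One reactor among 50 moves the arm mean by 1/50 of that patient's change. A 10 SD rise moves it 10/50 = 0.20 SD, inside ±0.39 SD. Reaching 0.39 SD would take 0.39 × 50 = 19.5 SD.

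A mean comparison is therefore informative about a shift shared by many patients, not about an isolated reaction.

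**The case against.** The strongest reply is that the plan already compares these events. Table 5 and its treatment-emergent, serious and related versions count them by arm, and the main Table 5 counts all AEs whatever their causality, so biased attribution to drug affects only the related-event version. This stands. What it leaves open is the earlier step: whether an abnormal value becomes an AE at all.

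Second, the general commitments in protocol 13.1 and section 6.10, with the latitude in section 6.6, could yield a by-arm laboratory summary. That is also fair, but none of them names an analyte, visit or statistic, and the section written for laboratory results specifies listings.

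Third, baseline-adjusted differences add modelling to a descriptive plan whose primary endpoint is the causality and severity of AEs. Estimates with intervals remain compatible with the protocol's decision not to test. A plain by-arm summary would be the minimum needed to deliver what is already promised.

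Three stronger readings are tempting and are not supported:
- A reader might infer that the plan has lost its one objective safety comparison. Table 6 gives deaths and SAEs by arm, and section 7.3 gives all-cause mortality by arm.
- A reader might infer that a by-arm laboratory comparison will never be made. The general clauses permit one; it is simply not specified.
- A reader might infer that laboratory summaries would detect the reactions reported below 1%. Step 4 shows that they would not. That figure also comes from surveillance of licensed use, not from measured values in COVID-19 patients.

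**Conclusion.** The point holds as a gap between commitment and output. The five analytes are scheduled in both arms and tied to named events of interest, but their values are only listed. The by-arm comparison that is specified runs through AE recording, which is an unblinded judgement without a numerical laboratory threshold.

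What is lost is an estimate of any common shift, to about ±0.39 SD with 50 sampled per arm or ±0.44 SD with 40. The first figure assumes full enrolment and complete sampling; the second is an illustrative assumption. Protocol 5.3.4 allows camostat to stop at Day 7 in recovered patients, so a Day 14 difference may be diluted. The documents do not show that recording was in fact biased, or that a shift is expected. This is a worthwhile, inexpensive improvement to the safety reporting, not a flaw that invalidates the AE tables.

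**What to change.** In sections 6.8 and 8.2 of the reporting plan, add for ALT, AST, GGT, platelets and potassium, in the safety population and by arm:

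- Values at baseline, Day 7 and Day 14, and baseline-adjusted change at Days 7 and 14, with the between-arm difference and 95% CI. Use the log scale for enzymes if they are skewed. Show the number sampled at each visit.
- A shift table from baseline to the worst scheduled post-baseline value against normal limits. Restrict it to scheduled visits, because extra samples on camostat under protocol 5.3.3 would give that arm more chances of an extreme value.

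Section 6.2 already defines the baseline laboratory value. State that the tables are descriptive and carry no significance tests.

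The cost is modest programming on data already collected. The downside is 5 analytes × 2 visits = 10 intervals, which must not be read as tests.
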